2 STUDY OBJECTIVE

The objective of this study is to determine the feasibility and acceptability of a 4-week mindfulness program adapted from MBSR for adults with CNCP treated in UNC clinics.

2.1 Primary Objectives:

- 1: Determine the feasibility of recruiting via pain management providers and online advertisement, retaining participants, session attendance, and online data collection of quantitative measures during a 4-week mindfulness program for adults with CNCP 2: Determine participant acceptability and satisfaction with the intervention using quantitative measure of intervention credibility and with individual semi-structured interviews.
- **Secondary Objective:** Assess preliminary effects of the intervention on self-reported functioning, quality-of-life, depressive and anxiety symptoms, pain severity and interference, and other psychological variables that have been shown to improve with mindfulness training and may have beneficial impacts on chronic pain management.

3 INVESTIGATIONAL PLAN (brief overview)

3.1 Study Design

This is a single-arm, mixed-methods, repeated-measures study of a 4-week mindfulness training program for adults being treated for CNCP within UNC pain management clinics.

Screening: Potential participants will hear about this study through their pain management providers (physician/PA/nurse/clinical pharmacist/mental health) or flyer advertisements, and interested patients will contact study personnel for complete a phone screening interview. If a participant is deemed eligible, the PI/research assistant will review the information in the consent form with the participant over the phone and answer any questions. Participants will provide written consent online via a REDCap survey link.

Baseline: Baseline measures will be completed by participants within the week prior to starting the intervention. Participants will receive an email with a link to a REDCap survey containing the self-reported questionnaires. Questionnaires should take approximately 30 minutes to complete. Intervention: The intervention will consist of four weekly, 1 hour and 30 minute group mindfulness training sessions. It will take place at a UNC clinic or conference room location. The intervention will be adapted from the standard 8-week MBSR program to fit the shorter class duration and to pertain specifically to chronic pain management. Mindfulness skills will include sitting meditation with attention to breathing, body scan meditation, mindfulness of daily routine activities, and expanding practice to notice and release fixation on thoughts, emotions, or sensations. Participants will be given guided audio recordings of mindfulness practices and course handouts and asked to complete home practice assignments daily during the course. They will also be sent a brief REDCap survey daily to record their daily home practice of mindfulness skills and daily pain intensity. Follow up: Post-intervention measures will be completed by participants via an online REDCap survey within one to two weeks after the final intervention session. Also within one to two weeks of the final intervention session, participants will be scheduled to complete a 20 to 30 minute semi-structured phone interview assessing their experience (satisfaction, challenges, suggestions for improvement) with the intervention.

3.2 Allocation to Treatment Groups and Blinding (if applicable)

Not applicable – all eligible participants who provide consent will be enrolled in the mindfulness training intervention. The first 12 eligible participants will be enrolled in one cohort, and the next 12 eligible participants will be enrolled in the second cohort receiving the same intervention.

3.3 Study Duration, Enrollment and Number of Subjects

If recruitment proceeds as planned, the study from the beginning of enrollment to the last point of data collection could last approximately 6 months. However, up to one year will allocated should there be any issues with recruitment that need to be resolved or there is a need to wait to enroll between the first and second cohorts because of the time of year (e.g. holidays that would interfere with intervention sessions occurring for 4 consecutive weeks). One year is the allowable funding period. Participants will be enrolled on a rolling basis as they learn about the study, contact the study PI, and complete screening and consent procedures. We will attempt to limit each recruitment period to approximately 4 to 6 weeks to reduce the likelihood of attrition resulting from a prolonged waiting period between enrollment and the start of the group intervention. 12 participants will be enrolled in each group for a total of 24 participants.

3.4 Study Population

Participants will be patients in UNC Clinics that assist with pain management, including but not limited to the Department of Anesthesiology Pain Clinic, the Spine Center, Physical Medicine and Rehabilitation, and Internal Medicine.

Inclusion Criteria

- 1. Adults aged 18 and older
- 2. Diagnosed with one or more CNCP conditions (daily pain for at least 3 months duration)
- 4. Established with one or more physician providers for pain management (e.g. primary care physician, pain specialist, etc).
- 5. Report more than minimal pain bothersomeness (>3 on 0-10 scale) and/or pain interference with activities (>2 on a 0-10 scale).
- 6. Able to read, understand and speak English

Exclusion Criteria

- 1. Diagnosis of mental illness with psychotic features
- 2. History of inpatient admission for psychiatric disorder in past 2 years
- **3.** Active substance abuse within the past year
- **4.** Has completed an MBSR or other mindfulness course; has or previously had a regular mindfulness meditation practice.
- **5.** Unable or unwilling to comply with study procedures (online questionnaires and practice diaries, 4 weekly intervention sessions, home practice, and one semi-structured phone interview).

4 STUDY PROCEDURES (what will be done)

See **Appendix A** for the schedule of evaluations.

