Study Objective(s)	 Primary To determine the feasibility and acceptability of a 4-week mindfulness training program adapted from MBSR for adults with CNCP recruited from UNC pain management clinics Secondary To test the preliminary effects of the mindfulness training program on pain-related, quality of life (QOL), and psychological outcomes. 						
Test Article(s) (If Applicable)	The intervention is based on MBSR, an 8-week mindfulness training program developed to help people manage stress-related and chronic conditions. The adapted mindfulness intervention will consist of four, weekly 1 hour and 30 minute group sessions that are modified from the original program to fit the shorter length and to directly address chronic pain management.						
Study Design	This feasibility study uses a single-arm, mixed-methods repeated measures design, with quantitative measures administered within 1 week pre and post-intervention, and qualitative semi-structured interviews administered within one to two weeks post-intervention.						
Subject Population	Inclusion Criteria						

key criteria for Inclusion and Exclusion:	Adults aged 18 and older who are able to read and speak English					
	Diagnosed with one or more CNCP conditions (daily pain at least 3 months duration) who report more than minimal pain bothersomeness and interference with activities					
	3. Has established care with provider who manages pain					
	Exclusion Criteria					
	 Diagnosis of mental illness with psychotic features 					
	History of inpatient admission for psychiatric disorder in past 2 years					
	3. Active substance abuse within the past year					
	 Completed an MBSR or other mindfulness course; has had a regular mindfulness practice during the course of the chronic pain condition 					
Number Of Subjects	24					
Study Duration	Each subject's participation will last up to 12 weeks including possible wait-time between screening and intervention start.					
	The entire study is expected to last up to 12 months.					
Study Phases Screening Study Treatment Follow-Up	(1) Screening : Phone screening with study personnel to determine eligibility for study. If eligible, the consent form will be reviewed with the participant over the phone and online written consent will be obtained after the phone call and before completing baseline measures.					
	(2) Baseline Measures: Administered via online self-report questionnaires					

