4.1 Screening procedures

Interested individuals will contact study personnel to complete a phone screening interview. Alternatively, if potential participants give permission to the referring provider to be contacted, the screener will initiate phone contact. The screener will provide individuals with a description of the study and the screening procedure and ask for permission from the individual to continue with the screening. If the individual provides verbal consent to the phone screening, they will be asked several questions to determine their eligibility based on age, chronic noncancer pain diagnosis, established care with physician, pain bothersomeness/interference, history of mindfulness training, psychiatric hospitalization, or psychosis, as well as active substance abuse in the past year. If they are deemed eligible based on the phone screening, the screener will verbally review the consent form with the individual, and written consent will be obtained following the phone call via an online consent form through REDCap. Individuals who provide online consent will be enrolled in the study.

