Appendix B. Measures

Scale or Item	Description
Screening Measures/Items	
Drug Abuse Screening Test ²⁷ (DAST)-10	10 items; assess drug use in the past 12 months
Alcohol Use Disorders Identification Test	3 items; assesses alcohol consumption, drinking
(AUDIT) ^{28,29}	behaviors, and alcohol-related problems
Chronic pain	Have you experienced pain on a daily basis for at least
	3 months?
Pain bothersomeness	How bothersome was your pain in the previous week?
	(rating scale 0-10).
Pain interference with general activities	How much did your pain interfere with your general
	activities in the past week? (rating scale 0-10).
Diagnosis of mental illness with psychotic	Have you ever been diagnosed with schizophrenia,
features	schizoaffective disorder, or another psychiatric
	disorder with psychotic symptoms?
Psychiatric hospitalization in past 2 years	Have you ever been hospitalized for mental health
	reasons? When was the last hospitalization?
Previous mindfulness training	Have you ever participated in mindfulness training or
	course? Have you ever had a regular mindfulness
	practice? When?
Baseline-only Measures	
Demographic variables	Age, race/ethnicity, education, income, marital status
Pain conditions and regions	e.g. fibromyalgia, osteoarthritis, low-back pain,
	migraine, neck pain, etc
Baseline and Post-test Measures*	
Pain Medication Use	Pain medications taking, frequency, and dose
Physical Function (short-form 4a) ³⁰	4 items; difficulty with activities of daily living
Anxiety (sf 4a)	4 items; suggestive of anxiety in the past 7 days
Depression (sf 4a)	4 items; suggestive of depressed mood in past 7 days
Sleep Disturbance (sf 4a)	4 items; sleep quality and disturbance in past 7 days
Pain Interference (sf 6b)	6 items; degree to which pain interferes with life
Pain Intensity	1 item; average pain intensity past 7 days (0-10)
Positive Affect and Wellbeing	9 items;
Perceived Stress Scale – 4	4 items; global measure of perceived stress
Pain Catastrophizing Scale ³¹	13 items; 3 subscales characterizing thoughts and
	feelings when in pain – rumination, magnification,
	helplessness
Chronic Pain Acceptance Questionnaire ³²	20 items; acceptance of experiencing pain
Freiberg Mindfulness Inventory	14 items; measures all aspects of mindfulness
Intervention Satisfaction	1 likert-type item asking how satisfied are with the
2.22	intervention oveall
Credibility Questionnaire ^{34,35} (after session	5 items assessing opinions about the intervention

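### Do the synopsis and Section 3.4 define two different eligible populations on past mindfulness practice and on pain?

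*Combined protocol and SAP*

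**What the plan says.** **Past practice.** The synopsis excludes people who completed a mindfulness course and, separately, anyone who "has had a regular mindfulness practice during the course of the chronic pain condition". Section 3.4 excludes a person who "Has completed an MBSR or other mindfulness course; has or previously had a regular mindfulness meditation practice", with no reference to when the pain began.

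**Pain.** The synopsis admits people "who report more than minimal pain bothersomeness and interference with activities" and gives no cut-offs. Section 3.4 asks that they "Report more than minimal pain bothersomeness (>3 on 0-10 scale) and/or pain interference with activities (>2 on a 0-10 scale").

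**Status of the two lists.** The synopsis labels its list "key criteria for Inclusion and Exclusion". Section 3.4 is the full list under the Study Population heading. No sentence says which governs if they differ.

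**Screening and enrolment.** Section 4.1 names the topics to be covered, including "pain bothersomeness/interference, history of mindfulness training", without a decision rule. The screening items in Appendix B ask "Have you ever had a regular mindfulness" practice, and then when. Section 3.2 states that "all eligible participants who provide consent will be enrolled in the mindfulness training intervention", in two cohorts of 12.

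**The concern.** Eligibility criteria should have one meaning. Section 3.2 takes every eligible person who consents, up to the cohort size, so the criteria decide who enters. Section 6.1 makes enrolling 12 people in 4-6 weeks the first feasibility measure, and that result describes whatever population the criteria define. Under Section 12 either the PI or a research assistant may screen. Two screeners working from different pages could reach opposite decisions on the same caller, each with text to support the decision.

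The practice criterion looks the more serious of the two. A label announcing key criteria can excuse an omission, but here the synopsis adds a time limit that Section 3.4 lacks. Past practice is also absent from the baseline measures in Appendix B and the baseline summaries in Section 6.3, and the phone-screening log in Appendix C gives a reason only for callers found ineligible. A mixed application of the rule might therefore not show in the reported data.

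**Working it through.** **Step 1. Past practice, case by case.** Chronic pain is current at screening, so any current practice falls within the pain condition.

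| Caller | Synopsis | Section 3.4 |
|---|---|---|
| Completed a mindfulness course | Excluded | Excluded |
| No course; regular practice now | Excluded | Excluded |
| No course; past practice, after pain began | Excluded | Excluded |
| No course; past practice, ended before pain began | Not excluded | Excluded |
| No course; never a regular practice | Not excluded | Not excluded |

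The two rules disagree in one row of five. Everyone whom Section 3.4 admits on this criterion is also admitted by the synopsis, so a screener using Section 3.4 enrols nobody whom the synopsis would bar on practice.

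**Step 2. Pain.** Take bothersomeness 6 and interference 0.

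- Section 3.4: 6 > 3 is true, so the *and/or* condition is met.
- Synopsis with Section 3.4's cut-offs borrowed (an assumption): 0 > 2 is false, so *and* is not met.
- Synopsis read as any interference at all, 1 or more (an alternative assumption): 0 ≥ 1 is false, so *and* is not met.

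The literal wordings therefore differ. With Section 3.4's cut-offs applied to both, and integer scores 0-10 on each item (11 × 11 = 121 pairs):

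- *and*: 7 bothersomeness values (4-10) × 8 interference values (3-10) = 56 pairs.
- *and/or*: 121 − (4 × 3) = 109 pairs, removing those with bothersomeness 0-3 and interference 0-2.
- Difference: 109 − 56 = 53 pairs.

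This counts possible scores. It says nothing about how many callers have them, because the documents give no distribution of screening scores. A screener could not apply the synopsis wording to the 0-10 items without borrowing a threshold, and the only thresholds in the document are those in Section 3.4.

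**Step 3. Whether any planned figure depends on the choice.** The inputs are those of Section 6.4.

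- Retention: half-width = 1.96 × √(0.85 × 0.15 / 24) = 0.143, giving (0.707, 0.993). The plan states 0.14 and (0.71, 0.99).
- Attendance: design effect = 1 + (4 − 1) × 0.10 = 1.3. Half-width = 1.96 × √(0.75 × 0.25 × 1.3 / 96) = 0.099, giving (0.651, 0.849). The plan states 0.10 and (0.65, 0.85).
- Post-test sample: 24 × 0.85 = 20.4, which agrees with the stated 20.

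All three reproduce. Their inputs are 24 participants, four sessions each, two assumed proportions and a correlation. None refers to either eligibility criterion.

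**Step 4. What could move.** Section 3.2 takes the first 12 eligible people and then the next 12, so total enrolment is 24 under either wording. Only the time taken to fill a cohort and its make-up could shift, and the documents offer nothing from which to size that shift.

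**The case for a change.** The strongest case for acting is the past-practice criterion. The synopsis states a different rule there, not a shorter one. The screening item's follow-up about timing sharpens this: timing matters only if some past practice is tolerated, so the screener collects the very fact on which the rules differ and is not told how to use it. The correction would cost a line of text, and a feasibility result is easier to carry into a larger trial when its population has a single definition.

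What stands is that the two sentences conflict literally for one kind of caller, and that no precedence statement resolves it. A tidy document would not have this.

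The rest is weaker. The synopsis is visibly a paraphrase: it omits the pain cut-offs and the exclusion for people unable or unwilling to comply, and it refers to a provider where Section 3.4 specifies physician providers. A reader applying criteria would naturally turn to the fuller list. That disposes of the pain point and lowers the practical risk on practice, though it does not explain the added time limit.

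The worry about invisible data is also overstated. Past practice is asked about at screening, and nothing shows that eligible callers' answers are discarded. A 14-item mindfulness inventory is completed at baseline. It measures current mindfulness and not practice history, so it is only a rough proxy.

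**Conclusion.** The concern does not call for a change to the plan. One literal mismatch is real: a regular practice that ended before the pain began, in someone who never completed a course. The pain wording is a side note, probably shorthand.

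The number of callers affected cannot be determined, and the practice case is narrow by construction. No endpoint definition, sample size, interval or analysis changes, and the results of a 24-person single-arm feasibility study would be sound under either wording. Making the synopsis and Section 3.4 agree is ordinary copy-editing, with no demonstrable gain for what the trial will report.

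This rests on two assumptions: that screeners work from the full criteria in Section 3.4, and that they apply one reading throughout. The conclusion takes no view on which past-practice rule was intended.

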4.1 Screening procedures

Interested individuals will contact study personnel to complete a phone screening interview. Alternatively, if potential participants give permission to the referring provider to be contacted, the screener will initiate phone contact. The screener will provide individuals with a description of the study and the screening procedure and ask for permission from the individual to continue with the screening. If the individual provides verbal consent to the phone screening, they will be asked several questions to determine their eligibility based on age, chronic noncancer pain diagnosis, established care with physician, pain bothersomeness/interference, history of mindfulness training, psychiatric hospitalization, or psychosis, as well as active substance abuse in the past year. If they are deemed eligible based on the phone screening, the screener will verbally review the consent form with the individual, and written consent will be obtained following the phone call via an online consent form through REDCap. Individuals who provide online consent will be enrolled in the study.

4.2 Baseline procedures

Participants will be emailed a link to a REDCap survey, where they will complete self-report questionnaires on 1) demographic information, 2) current pain medications and doses, 3) the PROMIS-29 Profile with physical functioning and health-related quality of life domains, depression, anxiety, pain interference/severity, 4) psychological variables including pain catastrophizing, pain acceptance, mindfulness, positive affect, and emotional and behavioral self-regulation. The survey should take approximately 30 minutes to complete.

4.3 Intervention procedures (by visits)

The mindfulness intervention will consist of four, weekly group mindfulness skills sessions each lasting 1 hour and 30 minutes. Each session will allow time for a 5-minute break in the middle. Sessions will be co-instructed by PI [name] and faculty advisor [name]. All sessions will take place at the same location. See **Appendix B** for session-by-session content and home practice assignments. Participants will receive guided audio recordings for mindfulness skills practice, in addition to a binder with course handouts. The instructor will send one email to each participant the day after each session summarizing the session content and home practice assignments and encouraging participants to complete the daily mindfulness practice diaries. Sessions will be recorded to monitor fidelity to the intervention protocol. Participants will be asked to complete daily home practice and pain intensity diaries between session weeks 1 and 4 via online REDCap surveys that will be sent by email on a daily basis.

4.4 Follow- up procedures (by visits)

Post-Test Questionnaires: After the final intervention session (week 4), participants will be emailed a link with a REDCap survey containing all of the questionnaires from the

baseline survey, excluding demographic information. It will also include questions on intervention credibility.

Post-Test Interview: With-in 1 to 2 weeks after the final session, participants will be scheduled for a 15 to 30-minute semi-structured phone interview with the PI to assess participants' experience with the intervention sessions and overall study. Questions will address the following: satisfaction and usefulness of the skills and content, acceptability of the format, any challenges, and any suggestions for improvement of the intervention or study procedures.

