1.2 Name and Description of Investigational Product or Intervention

The current study will use an adapted version of the established mindfulness training program called Mindfulness-based Stress Reduction (MBSR). MBSR is the most popular and well-tested format for teaching mindfulness skills in the U.S. MBSR was developed by [name] to teach a range of mindfulness skills to help individuals better manage chronic and stress-aggravated illnesses.^{20,21} Mindfulness skills involve the intentional self-regulation of attention to present-moment experience, combined with releasing cognitive fixation on thoughts and emotions regarding the past or future.¹³ The MBSR program teaches a range of mindfulness-related skills, typically in an eight-week, 2.5 hour per week group format, with a 6-hour weekend day of mindfulness retreat. It is generally available to medical patients and community members with a wide range of stress-related problems or medical conditions. The current study will use an adapted version of this program, adapted by PI [name] and Faculty Advisor [name]. It will be adapted to fit the shorter length (4 weeks; 1 hour, 30 minute sessions) and will be directly related to chronic pain management and coping. See **Appendix B** for a breakdown of sessions content and mindfulness skills taught.

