6.1 Primary Endpoint

The primary outcomes are feasibility and acceptability of the intervention and study procedures. Feasibility will be assessed as 1) ability to enroll 12 participants for one intervention group within 4-6 weeks, 2) participant retention, with a goal of 85% retention, 3) session attendance, with a goal of 75% sessions attended, 4) proportion of completed assessments and practice forms.

Acceptability will be assessed via credibility questionnaire and semi-structured interview assessing satisfaction with the intervention, barriers to engagement, and suggestions for improving the intervention or study procedures.

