12 CONSENT PROCESS

Individuals will complete phone screening with the PI or RA. Participants will be given information about the nature of the phone screening and asked if they give permission to continue with the phone screen. If an individual is eligible for the study, the screener will review the information provided in the consent form with the individual over the phone, including the purpose of the research, the nature of involvement, the estimated risk of involvement, the potential benefits of participation, the right to stop participation at any time, and who to contact with questions about the research or consent process. The individual will have the opportunity to ask any questions over the phone. They will then be sent an email with the link to the online consent form, asked to read the consent form, and if they agree to participate, to sign the online consent form. Participants will have the opportunity to contact study staff to ask additional questions after reading the online consent form and before signing it.

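### The PI, who co-teaches and co-adapted the program, also conducts the acceptability interview, so one of two named measures of a primary outcome is likely to lean favourable, by an unknown amount

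*Combined protocol and SAP*

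**What the plan says.** On outcomes, section 6.1 states: "The primary outcomes are feasibility and acceptability of the intervention and study procedures". It measures acceptability by a credibility questionnaire and a "semi-structured interview assessing satisfaction with the intervention, barriers to engagement, and suggestions for improving the intervention or study procedures".

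On who interviews, section 4.4 provides for a "semi-structured phone interview with the PI to assess participants' experience with the intervention sessions and overall study", held one to two weeks after the last session. The topics are "satisfaction and usefulness of the skills and content, acceptability of the format, any challenges, and any suggestions for improvement".

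On the PI's other roles, section 4.3 says "Sessions will be co-instructed by PI", together with the faculty advisor; the synopsis and section 7 agree. Section 1.2 says the same two people adapted the program from MBSR.

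On other staff, section 12 says "Individuals will complete phone screening with the PI or RA", and section 3.1 lets the research assistant (RA) review the consent form with participants. Section 9 identifies the PI and faculty advisor as the instructors and lists the RA separately.

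On analysis, section 6.3 treats the interviews by qualitative description with a codebook. It does not say who codes.

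**The concern.** The person asking for the assessment taught the sessions and helped to write them. Participants have just spent four weeks in a small group with that person. Courtesy toward a teacher works in one direction: more satisfaction is expressed, and fewer complaints are made about instructor, content or format.

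What is most exposed is what the interview is best placed to supply: barriers, challenges and suggestions for change. Sections 6.4 and 13 say the results will help plan a larger trial and support grant proposals, so a fault that participants keep to themselves is carried forward. More participants would not remove the problem, and no confidence interval would show it.

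Section 9 also names the post-intervention interview among the routes for reporting unwanted experiences. Reluctance to criticise could therefore extend to discomfort caused by the practice, although that route is one of several.

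**Working it through.** The point is about design, so most of the check sets the provisions side by side.

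**1. Are the roles as described?** Yes. Interviewer: the PI (4.4). Instructor: the PI, jointly (synopsis, 4.3, 7). Adapter of the program: the PI, jointly (1.2). Status of the measure: one of two named for acceptability, a primary outcome (6.1).

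**2. Which acceptability data bypass the interviewer?**
- The measures appendix (headed Appendix B) lists a five-item credibility questionnaire and one Likert-type item on overall satisfaction. Both are closed ratings that participants complete themselves.
- The schedule in Appendix A marks satisfaction, barriers and suggestions under the online post-test survey as well as the interview. No survey instrument in 4.4 or the measures appendix collects barriers or suggestions.
- The case report forms record reasons for missed sessions and for withdrawal, which is a narrow view of barriers.
- Section 10 ties survey links to a participant identifier and gives the PI access to the file linking identifiers to names. The self-completed answers are therefore not anonymous to the PI.

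**3. Which primary results do not depend on the interview?** The section 6.4 figures can be reproduced without it:
- Retention: 1.96 × √(0.85 × 0.15 / 24) = 0.143 (plan: 0.14).
- Attendance: design effect 1 + (4 − 1) × 0.10 = 1.30; 1.96 × √(0.75 × 0.25 × 1.30 / 96) = 0.099 (plan: 0.10).
- Number at post-test: 24 × (1 − 0.15) = 20.4 (plan: 20).

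These rest on enrolment, status and attendance records. Who interviews does not alter them.

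**4. How could reticence affect the content?** The documents give no size for an interviewer effect, so this is illustration on assumed values. Suppose each of 20 interviewees independently holds a given criticism with probability f, and a holder voices it with probability d. The chance that no interview mentions it is (1 − f × d)^20.

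| f | d | Calculation | Chance never mentioned |
|---|---|---|---|
| 0.10 | 1 | 0.90^20 | 12% |
| 0.10 | 0.50 | 0.95^20 | 36% |
| 0.10 | 0.25 | 0.975^20 | 60% |
| 0.20 | 1 | 0.80^20 | 1% |
| 0.20 | 0.50 | 0.90^20 | 12% |
| 0.20 | 0.25 | 0.95^20 | 36% |

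With about 20 interviews, a less common criticism can be missed even under full candour, and reticence raises that chance. The value of d is unknown.

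**5. What would a change of interviewer cost?** 24 × 15 min = 6 hours; 24 × 30 min = 12 hours. Section 3.1 gives 20 to 30 minutes instead, which makes 8 to 12 hours.

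**The case against.** The strongest reply is that this is a 24-person, single-arm feasibility study that disclaims any test of efficacy. Its numerical goals do not use the interview, and the interview yields a descriptive summary with no pass mark. Other acceptability data exist. The PI is a clinical psychologist trained in pain psychology, which helps both with probing and when an interview brings up distress. The interview guide and consent form are not in the text available, so an assurance to participants may appear there.

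Much of this stands, and it limits the point. A reader might infer any of the following, and the documents do not support them:
- *That nothing in the plan offsets the problem.* The credibility and satisfaction items do so in part, as do attendance, retention and practice-form completion.
- *That the feasibility conclusion is compromised.* Its goals come from records, not from the interview.
- *That a control group would have exposed the bias.* It would not show whether people soften answers to their own instructor; that takes a different interviewer or an anonymous measure.
- *That satisfaction is inflated by some number of percentage points.* Section 6.3 does not plan to derive a percentage from the interviews, and any such figure would rest wholly on assumed inputs.

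The reply does not remove the core. The remaining sources are closed ratings or narrow records, and the interview is the only specified instrument that asks about barriers and suggestions across the program.

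**Conclusion.** The point holds for the interview component of acceptability. As written, the plan has an instructor and co-author of the program ask participants to assess it. The roles are certain from the text. The direction, toward higher satisfaction and fewer criticisms, is an inference from ordinary behaviour toward a teacher and is likely rather than proven. The size cannot be derived from the documents. All planned interviews are affected: up to 24, or about 20 at the assumed 15% dropout. Classed as a cheap improvement, best made before the first interviews, because answers already given to the instructor cannot be corrected later.

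**What to change.** In section 4.4, replace the PI as interviewer with the research assistant, and state that this person does not teach the sessions. The PI may still write the interview guide.

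Tell participants at the start that their comments on the program will reach the instructors only in de-identified form, with one stated exception: any unwanted experience or adverse event will be passed to the PI identifiably. Without that exception the promise would conflict with section 9, which makes the interview a reporting route and has the PI gather, record and report such events.

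If the PI must interview, report this as a limitation of the acceptability result.

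Cost: about 6 to 12 hours of RA phone time, plus set-up, brief training and de-identification of notes or transcripts. The documents do not say that interviews are recorded or transcribed, so the last item depends on how they are captured. They also do not give the RA's interviewing experience or available hours; that existing staff can absorb the work is an assumption. Downside: probing may be less expert than the PI's. Sample size, visits and participant burden do not change.
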